12.4.2 Statistical model, hypothesis, and method of analysis

For all safety analyses, the safety set will be used. All listings and tables will be presented by treatment group. Graphical representations of the safety data may be produced.

Adverse events

All information obtained on adverse events will be displayed by part, treatment group and subject. The number and percent of patients with adverse events will be tabulated by system organ class and preferred term with a breakdown by treatment group. A subject with multiple adverse events within a system organ class is only counted once towards the total of the system organ class. Separate tables and listings will present adverse event severity (CTCAE grade) and relationship to study treatment.

The number (and percent) of subjects with adverse events of infusion site reaction may be summarized by treatment group.

Vital signs

If normal ranges are available, vital signs abnormalities (and relevant orthostatic changes) will be flagged and will be listed by part, subject and visit/time. Summary statistics may be provided by part, treatment group and visit/time.

ECG evaluations

Abnormal ECG data will be flagged and will be listed by part, treatment group, subject and visit/time. Summary statistics may be provided by part, treatment group and visit/time.

Holter ECG data analysis

The relationship between change from baseline in time-matched QTcF and KAE609 plasma concentration will be explored using linear mixed effects modeling. Other ECG parameters (QT, QTcB, HR, PR interval and QRS) will be summarized. Data from the SAD and MAD parts of the study will be pooled for this assessment. The change from baseline in QTcF will be the dependent variable in the model, KAE609 plasma concentration will be a covariate, and time a categorical variable. A random intercept for each subject will be specified. Placebo subjects will be included in the analysis with a plasma concentration of 0. The placebo-corrected change from baseline in QTcF and the two-sided 90% confidence interval will be extracted from the model at the geometric mean maximum plasma concentration for each treatment.

A plot of raw QTcF change vs KAE609 plasma concentration will be presented together with the estimated slope and 90% Confidence Interval (CI) from the statistical model.

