7.2 Descriptive analyses

Subject demographics and other baseline characteristics

All data for background and demographic variables will be listed by part, treatment group and subject. Summary statistics will be provided by part and treatment group.

Relevant medical history, current medical conditions, results of laboratory screens, drug tests and any other relevant information will be listed by part, treatment group and subject.

Treatment

Data for study drug administration (rescue medication) and concomitant therapies will be listed by part, treatment group and subject.

Vital signs

All vital signs data will be listed by treatment, subject, and visit/time and if ranges are available abnormalities (and relevant orthostatic changes) will be flagged. Summary statistics will be provided by part, treatment and visit/time.

ECG evaluations

All ECG data will be listed by treatment, subject and visit/time, abnormalities will be flagged. Summary statistics will be provided by part, treatment and visit/time.

Clinical laboratory evaluations

All laboratory data will be listed by treatment, subject, and visit/time and if normal ranges are available abnormalities will be flagged. A separate listing is provided presenting all parameters in a subject with any abnormal values. Summary statistics will be provided by part, treatment and visit/time.

Local tolerance at infusion site

Local tolerance at infusion site will be summarized by part and treatment group.

Adverse events

All information obtained on adverse events will be displayed by part, treatment and subject.

The number and percentage of subjects with adverse events will be tabulated by system organ class and preferred term with a breakdown by treatment, and separately by preferred term and treatment. A subject with multiple adverse events within a system organ class is only counted once towards the total of this system organ class and treatment.

The number and percentage of subjects with adverse events by maximum severity of adverse events will be tabulated by system organ class and preferred term with a breakdown by treatment.

The number and percentage of subjects with adverse events classified as related to study drug will be tabulated by system organ class and preferred term with a breakdown by treatment.

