For the legal requirements of ClinicalTrials.gov and EudraCT, two required tables on all <on-treatment/treatment emergent> adverse events which are not serious adverse events and on all <on-treatment/treatment emergent> serious adverse events and SAE suspected to be related to

study treatment will be provided by system organ class and preferred term on the safety set population.

If for a same subject, several consecutive AEs (irrespective of study treatment causality, seriousness and severity) occurred with the same SOC and PT:

- a single occurrence will be counted if there is ≤ 1 day gap between the end date of the preceding AE and the start date of the consecutive AE
- more than one occurrence will be counted if there is > 1 day gap between the end date of the preceding AE and the start date of the consecutive AE.

For occurrence, the presence of at least one SAE / SAE suspected to be related to study treatment / non SAE has to be checked in a block e.g., among AE's in a ≤ 1 day gap block, if at least one SAE is occurring, then one occurrence is calculated for that SAE.

The number of deaths resulting from SAEs suspected to be related to study treatment and SAEs irrespective of study treatment relationship will be provided by SOC and PT.

Holter ECG data analysis

The relationship between change from baseline in time-matched QTcF and KAE609 plasma concentration will be explored using linear mixed effects modeling. Other ECG parameters (QT, QTcB, HR, PR interval and QRS) will be summarized. Data from the SAD and MAD parts of the study will be pooled for this assessment. The change from baseline in QTcF will be the dependent variable in the model, KAE609 plasma concentration will be a covariate, and time a categorical variable. A random intercept for each subject will be specified. Placebo subjects will be included in the analysis with a plasma concentration of 0. The placebo-corrected change from baseline in QTcF and the two-sided 90% confidence interval will be extracted from the model at the geometric mean maximum plasma concentration for each treatment.

A plot of raw QTcF change vs KAE609 plasma concentration will be presented together with the estimated slope and 90% Confidence Interval (CI) from the statistical model.

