7.3 Graphical presentation

Boxplots to visualize trends in longitudinal safety data (vitals, ECG, lab parameter) will be created.

8 Statistical methods for biomarker data

Not applicable.

9 Exploratory objectives

Commercially Confidential Information

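### Cheap improvement: report the concentration-QTcF model with an active/placebo term beside the planned one, because as planned every treatment's effect and 90% CI is one slope multiplied by Cmax

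*SAP*

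**What the plan says.** The Holter ECG paragraph of SAP 7.2 takes the change from baseline in QTcF as the dependent variable and lists the model terms: "KAE609 plasma concentration will be a covariate, and time a categorical variable. A random intercept for each subject will be specified". Protocol 12.4.2 gives the same model ("A random intercept for each subject will be specified"). No active/placebo term is listed in either place, and neither paragraph shows a redaction.

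Three further statements determine what the model can deliver:

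- Coding of placebo: "Placebo subjects will be included in the analysis with a plasma concentration of 0".
- Pooling, so that one slope serves every dose group: "Data from the SAD and MAD parts of the study will be pooled for this assessment".
- The reported quantity, a placebo-corrected change with a two-sided 90% CI: "extracted from the model at the geometric mean maximum plasma concentration for each treatment".

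Some descriptive output could hint at a poor fit. The SAP plans a plot ("A plot of raw QTcF change vs KAE609 plasma concentration will be presented together with the estimated slope and 90% Confidence Interval"), ECG listings and summaries ("abnormalities will be flagged. Summary statistics will be provided by part, treatment and visit/time") and graphs ("Boxplots to visualize trends in longitudinal safety data (vitals, ECG, lab parameter) will be created"). Protocol 12.4.4 lists no sensitivity or supportive analyses. SAP 7.2 also announces a separate cardiac safety report.

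**The concern.** The plan presents a QTcF result for each treatment. With only a common slope and placebo fixed at 0, those results are one estimate shown at seven scales. A low-dose group then gets a very narrow interval because the model forces the effect to zero at zero concentration, not because six subjects at that dose supply that much information.

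QTcF is part of the primary endpoint (Protocol Table 2-1 and 12.4.1), this is the first iv study, and this is the only placebo-corrected QTcF estimate with a CI in the visible text. Protocol 4.1 cites a hERG finding and the absence of a QTcF effect with oral dosing. A bolus or a 10-minute infusion (Protocol 6.7) is a new exposure profile, so proportionality to concurrent concentration is an assumption here. If it fails, the descriptive plots may suggest so, but the reported estimates and intervals will not show it.

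**Working it through.** **Inputs from the documents.** Part A has 5 cohorts with 6 active and 2 placebo each; Part B has 2 cohorts with 6 active and 3 placebo each. Active: 5 x 6 + 2 x 6 = 42. Placebo: 5 x 2 + 2 x 3 = 16. The total of 58 matches Protocol section 5. (SAP 1.4 also mentions four Part A cohorts, which would give 4 x 8 + 2 x 9 = 50; the algebra below does not depend on this.) Part B doses are 60 and 120 mg; Part A doses are redacted.

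**The plan's own figures.** None is given for the QTcF model. The only design calculation, Protocol Table 12-2, reproduces: 1 - 0.8^6 = 73.8%, stated as 74%.

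**Algebra.** The planned model is dQTcF_ij = time_j + b x C_ij + u_i + e_ij. At the same time point, active at Cmax minus placebo at 0 is:

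- effect = b x Cmax
- 90% CI = Cmax x (b_hat ± crit x SE(b_hat))

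The effect/SE ratio is b_hat/SE(b_hat) for every treatment, so either all seven intervals exclude 0 or none does. With an active/placebo term theta:

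- effect = theta + b x Cmax
- variance = Var(theta) + Cmax^2 x Var(b) + 2 x Cmax x Cov(theta, b)

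This part is exact and needs no assumption about PK or variances.

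**One simulated data set as a check** (assumed doses and PK, arbitrary concentration units):

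| Group | Cmax | Planned effect (90% CI) | Effect/SE | With term (90% CI) | Effect/SE |
|---|---|---|---|---|---|
| A1 | 9.4 | 0.38 (0.25, 0.52) | 4.590 | 2.55 (0.26, 4.83) | 1.834 |
| B1 | 78.0 | 3.18 (2.04, 4.32) | 4.590 | 4.99 (2.78, 7.20) | 3.711 |
| A5 | 212.7 | 8.68 (5.57, 11.78) | 4.590 | 9.78 (6.49, 13.08) | 4.886 |

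Under the planned model every effect is 0.04079 x Cmax.

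**Size, which rests on assumptions.** Not in the documents and assumed: residual SD 6 ms, subject SD 4 ms, biexponential PK with half-lives 0.5 h and 24 h, concentration CV about 30%, Part A doses 10, 30, 75, 120 and 210 mg, and Part B sampled as Part A on Days 1 and 5. There were 2,000 runs per scenario. Levelling off means 8 ms at the top dose and half-maximal at 25% of top Cmax.

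| | Lowest dose | B1 | B2 | Top |
|---|---|---|---|---|
| Proportional: 90% CI width, planned (ms) | 0.35 | 2.4 | 4.3 | 6.5 |
| Proportional: 90% CI width, with term (ms) | 4.4 | 4.6 | 5.6 | 7.2 |
| Levelling off: truth (ms) | 1.8 | 5.9 | 7.2 | 8.0 |
| Levelling off: planned estimate (ms) | 0.4 | 2.8 | 5.1 | 7.7 |
| Levelling off: planned coverage | 0% | 2% | 47% | 89% |
| Levelling off: estimate with term (ms) | 2.1 | 4.3 | 6.4 | 8.8 |
| Levelling off: coverage with term | 89% | 68% | 84% | 88% |

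In the proportional case both models cover 89-91%.

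Two smaller repeats with other PK weights (600 and 250 runs) gave planned coverage under levelling off of 0%, 0%, 48-53% and 86-87%, with B1 at 72-74% once the term is added. Varying residual SD (5-8 ms), subject SD (3-6 ms), distribution half-life (0.25-1 h) and dose range (9-fold) gave planned coverage of 0%, 1-9%, 23-62% and 86-90%. With the term it was 83-88%, 59-75%, 75-85% and 86-89%.

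**Constant offset.** With a 3 ms active-placebo offset, planned coverage was 0%, 1-2%, 57% and 79-82%; with the term it was 89-93%. With 1.5 ms, planned coverage was 0%, 41%, 74% and 86%; with the term, 89-91%.

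**Lag.** With a 0.5 h effect half-life, the top-dose estimate is 48% of the true peak as planned and 57% with the term.

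**The term as a check.** Its SE is 1.35 ms. Its 90% CI excludes 0 in 10% of runs when the effect is proportional, 36% when it levels off, 31% with a 1.5 ms offset and 71% with 3 ms.

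**The case against.** The strongest reply is that this is a modelling preference. Zero effect at zero concentration is a natural constraint. The Protocol summary calls the study exploratory, and SAP 7.2 says this relationship is to be explored. The QT stopping criterion in Protocol 9.1.4 uses individual values, so no decision rule depends on this interval. Protocol 4.1 expects no QT effect, and if there is none both models are unbiased. All of this stands.

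The reply is also right that coverage alone flatters the term. When the effect levels off, RMSE at the lowest dose was 1.1-1.3 ms as planned and 1.5-1.7 ms with the term; at the top dose it was 2.2 and 2.3 ms. With no drug effect, lowest-dose RMSE rises from 0.1 to 1.3 ms. The gain in RMSE is at B1 (3.3 to 2.0 ms) and B2 (2.7 to 1.9 ms). Much of the recovered low-dose coverage comes from a wider interval.

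A reader might infer that the planned model is wrong and should be replaced. The documents do not support that: it is valid and tighter under proportionality, and nothing in them shows that proportionality fails. A reader might also infer that no check is planned. Protocol 12.6 and SAP 9 are redacted and a cardiac safety report is to be written separately, so one may exist. Neither possibility changes the model that SAP 7.2 states.

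**Conclusion.** The point holds as a low-cost improvement to an exploratory analysis, not as an error. That each treatment's effect and 90% CI is a rescaled slope is exact. How much this matters depends on assumed PK, variances, Part A doses and effect shape.

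Under those assumptions, the planned intervals at the lowest dose, B1 and B2 under-cover badly if the effect levels off or there is an offset; with an offset the top dose is affected too. A lowest-dose interval about 0.3 ms wide is a product of the constraint. It would be an over-reading to treat the extra term as a cure. It corrects levelling-off only in part (B1 coverage about 68-74% in the base-case runs), gains little or nothing at the top dose in that case, and does not remedy lag. Nor does a term near 0 prove proportionality, because the check has limited power.

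**What to change.** In SAP 7.2 and Protocol 12.4.2, pre-specify a second fit of the same model with an active/placebo fixed effect. From it, extract treatment effect + slope x geometric mean Cmax with its 90% CI for each treatment. Report this beside the planned model, together with the treatment term and its 90% CI, and state that neither model will be selected on that term's significance. Protocol 12.4.4 would need a matching line. If the cardiac safety report or a redacted section already contains this fit, a cross-reference in SAP 7.2 is enough.

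The cost is one extra fit and one contrast, one degree of freedom, and no new data. The second fit is less precise: in simulation the 90% CI widened about 0.3 to 4.5 ms at the lowest dose and 6.5-6.9 to 7.2-7.4 ms at the top, with larger RMSE at the lowest dose. Keeping the planned fit in the report leaves the tighter estimate visible. Random concentration slopes and by-time intervals are not part of this fix.

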1.2 Purpose

The purpose of this study is to assess the safety and tolerability and pharmacokinetics (PK) of single ascending doses (SAD) and multiple ascending doses (MAD) of KAE609 administered by iv infusion in healthy subjects, to support further clinical development of KAE609 in patients with severe malaria and to guide dose selection for future trials.

2 Objectives and endpoints

Table 2-1 Objectives and related endpoints

Objective(s)	Endpoint(s)
Primary objective(s)	Endpoint(s) for primary objective(s)

 To assess the safety and tolerability of single and multiple iv doses of KAE609 in healthy subjects 	
 Adverse events, physical examination findings, vital signs, ECG findings (including QTcF), safety laboratory assessments including chemistry, hematology, and urinalysis results
Secondary objective(s)	Endpoint(s) for secondary objective(s)

 To assess the pharmacokinetics (PK) of single and multiple iv doses of KAE609 in healthy subjects 	
 AUC, Tmax, Cmax, CL, Vz, and T1/2

 To assess local tolerance at infusion site of KAE609 iv administration 	
 Findings of physical examination of infusion site

Commercially Confidential Information

3 Study design

This is a randomized, subject and investigator-blinded, placebo-controlled, single and multiple ascending iv dose study in healthy subjects. The study consists of two parts and the study scheme is shown in [Figure 3-1](#):

- Part A is a single ascending dose (SAD) study with 5 cohorts of 8 subjects each
- Part B is a multiple ascending dose (MAD) study with 2 cohorts of 9 subjects each

For both parts of the study, each subject will participate in an up to 28- day screening period during which a full physical examination, medical history, drug screening, vital signs, ECG evaluation and safety laboratory tests evaluation will be performed.

A review of safety and PK data will be conducted at the completion of each cohort prior to dosing of the next subsequent cohort. Please also refer to [Section 6.5.1](#) for more details on dose escalations. Safety assessments will include physical examinations, ECGs, vital signs, standard clinical laboratory evaluations (hematology, blood chemistry, urinalysis) adverse event and serious adverse event monitoring.

Commercially Confidential Information

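### The concentration-QTcF model has only a random intercept, so its 90% CIs are too narrow if the slope differs materially between subjects

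*SAP*

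**What the plan says.** SAP 7.2 and Protocol 12.4.2 describe the same Holter analysis under the same subheading. The relationship "will be explored using linear mixed effects modeling", with change from baseline in QTcF as the outcome.

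- Fixed effects: "KAE609 plasma concentration will be a covariate, and time a categorical variable".
- Random effects: "A random intercept for each subject will be specified".
- Data: "Data from the SAD and MAD parts of the study will be pooled for this assessment", and "Placebo subjects will be included in the analysis with a plasma concentration of 0".
- Output: the placebo-corrected change and "the two-sided 90% confidence interval will be extracted from the model at the geometric mean maximum plasma concentration for each treatment". A plot also shows the slope with its own 90% CI.

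The visible text names no random slope, robust standard error, degrees-of-freedom method or check for slope differences. Protocol 12.4.4 plans no sensitivity analyses. The graphical model check in SAP 5.3.1 belongs to the PK section. SAP 7.2 announces a separate cardiac safety report, whose content is not shown.

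**The concern.** Both reported intervals rest on the standard error of the slope. A random intercept takes up a shift that is constant within a subject. It cannot take up a deviation that grows with that subject's concentration. Each active subject contributes several ECGs matched to PK draws, and in Part B does so on two days. If sensitivity differs between subjects, those ECGs share a deviation that the model counts as independent residual noise, and the standard error comes out too small.

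The error is in the unsafe direction, because the upper limit of the QTcF effect is understated. QTcF is among the primary safety endpoints. Protocol 4.1 mentions a hERG signal, and Protocol 4.5 says that this is the first intravenous study and is meant to go above the doses foreseen for treatment.

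**Working it through.** **1. The plan's own figure.** The documents give no precision figure for the QTcF model. The only sizing figures are in Protocol Table 12-2, for adverse events in 6 active subjects. At a rate of 1 in 5, P(at least 1) = 1 − 0.8^6 = 1 − 0.262 = 73.8%, against the printed 74%. The other rows also agree within rounding. None of them bears on the slope.

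**2. Layout, from the documents.** "Part A is a single ascending dose (SAD) study with 5 cohorts of 8 subjects each" (Protocol Section 3), with 6 active and 2 placebo per cohort. Part B has 2 cohorts of 9, with 6 active and 3 placebo.

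- Active: 5 × 6 + 2 × 6 = 42. Placebo: 5 × 2 + 2 × 3 = 16. Total: 58.
- ECG times follow the PK draws (Protocol 8.4.3). Simulated: 10 and 30 min, 1, 3, 6, 12 and 24 h, on Day 1 in Part A and on Days 1 and 5 in Part B.

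**3. Mechanism.** Let subject i have slope β + u_i, where u_i has SD τ. The planned model sets τ = 0. The subject's deviation splits as u_i·C_ij = u_i·C̄_i + u_i·(C_ij − C̄_i). The intercept can take up the first part; the second goes into the residual. Approximately,

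Var(slope estimate) = (variance with equal slopes) + τ²·Σw_i², with Σw_i = 1,

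where w_i is subject i's weight in the estimate. The extra term depends on τ and not on β, so the condition is slope variability and not a nonzero mean effect.

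**4. Simulation of the planned layout.** Assumptions not in the documents: relative Part A doses 0.05, 0.14, 0.29, 0.57 and 1; Part B 0.29 and 0.57; biexponential PK with 30% between-subject variability; intercept SD 5 ms; residual SD 6 ms. One concentration unit is roughly the top single-dose peak, so a mean slope of 10 is about 10 ms there. There were 1000 runs per row, fitted by REML, with CI = estimate ± 1.645 SE. Monte Carlo error is about 1 to 1.5 points. The half-width needed is 1.645 × the empirical SD of the estimate.

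| Mean slope | Slope SD | Half-width, intercept only | Half-width needed | Coverage, intercept only | Coverage, random slope |
|---|---|---|---|---|---|
| 0 | 0 | 3.66 | 1.645 × 2.284 = 3.76 | 88% | 89% |
| 10 | 0 | 3.69 | 1.645 × 2.143 = 3.53 | 92% | 91% |
| 20 | 0 | 3.69 | 1.645 × 2.237 = 3.68 | 90% | 89% |
| 10 | 2.5 | 3.68 | 1.645 × 2.339 = 3.85 | 88% | 89% |
| 10 | 5 | 3.71 | 1.645 × 2.813 = 4.63 | 81% | 87% |
| 10 | 10 | 3.84 | 1.645 × 3.983 = 6.55 | 67% | 88% |
| 0 | 5 | 3.72 | 1.645 × 2.888 = 4.75 | 80% | 86% |
| 0 | 10 | 3.85 | 1.645 × 4.142 = 6.81 | 63% | 86% |
| 20 | 10 | 3.82 | 1.645 × 3.943 = 6.49 | 67% | 88% |

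At mean slope 10 the planned interval is 1 − 3.68/3.85 = 4%, 1 − 3.71/4.63 = 20% and 1 − 3.84/6.55 = 41% too narrow at slope SD 2.5, 5 and 10. The two rows with mean slope 0 and variable slopes show the same shortfall without any mean effect.

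**5. Other assumed doses and PK, same layout, 10 ms effect (intercept only against random slope).**

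- Assumed Part A range 10 to 240 mg, two-compartment PK, 700 to 900 runs: 87% v 90% at slope CV 30%; 81% v 91% at CV 50%, where the model SE is 2.09 ms against a true SD of 2.61 ms. A 5 ms effect at CV 50% (400 runs) gave 84% v 86%.
- A further set with 150 runs per case: 89% v 91% with equal slopes, 90% v 91% at CV 30%, 82% v 91% at CV 50%, 69% v 88% at CV 100%.
- A further set with 300 runs at CV 50%: 79% v 89%. With 117 runs at CV 30%: 88% v 90%.

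**6. How many subjects carry the slope.** All 42 active subjects do, with unequal weight. From step 3, Σw_i² = (3.983² − 2.143²)/10² = (15.86 − 4.59)/100 = 0.113 at mean slope 10, which is the information of about 1/0.113 = 9 equally weighted subjects. The figure depends on the assumed doses.

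**7. Behaviour of the remedy.** With equal slopes the random slope widened the interval by 3.80/3.66 − 1 = 4%, 3% and 2% in the first three rows of the table (random-slope half-widths 3.80, 3.79 and 3.78). Under the other assumptions it was about 4%, and 2.18/2.06 − 1 = 6%. In the last set of step 5 the slope variance was estimated at essentially zero in 24% of runs at CV 50% and 43% at CV 30%. There, a random-intercept fit with a subject-clustered robust SE covered 85% and 86%.

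**The case against.** A random intercept is a stated and parsimonious choice for an exploratory model. Protocol 4.1 expects no QT effect and reports none with oral KAE609. At a slope CV of 25 to 30% the loss is 3 points or less and hard to tell from simulation error. No document gives a slope CV. All of this stands, and it limits the size of the point.

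The consequence is also limited. No threshold for the CI appears in the visible text. The QTcF stopping rule in Protocol 9.1.4 uses individual values and increases. The categorical outlier and T-wave summaries do not use the model.

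Three stronger readings are tempting, and the documents do not support them:

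- **The CI is too narrow whenever KAE609 has a QTcF effect.** With a common slope, coverage stays near 90% at mean slopes of 10 and 20. With variable slopes it falls even at a mean of zero.
- **The effective sample is the 6 active subjects of the top cohort.** The parts are pooled, and all 42 active subjects inform the slope, though unequally.
- **The plan would wrongly rule out a relevant QTcF effect.** With no stated threshold, the plan does not formally rule anything out.

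What survives is that nothing visible in either document would detect or allow for slope differences.

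**Conclusion.** The point holds in conditional form, as a cheap improvement. That the model has only a random intercept is certain from both documents. How far the intervals fall short cannot be fixed from them. Under the assumptions shown, the shortfall is negligible with equal slopes, small at a slope CV of 25 to 30%, about 8 to 11 points of coverage at 50%, and above 20 points at 100%. A random slope recovers most of it, to 87 to 91% for a 10 ms effect and 86% in the zero-effect rows with variable slopes and in the 5 ms case. The remaining gap is partly due to the normal quantile: a t quantile with about 40 degrees of freedom gave 87 to 92% in the tabulated simulations. These figures assume normally distributed slopes and a linear concentration effect.

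**What to change.** In SAP 7.2 and Protocol 12.4.2, specify subject-level random effects for both the intercept and the concentration slope, with Kenward-Roger or Satterthwaite degrees of freedom for the 90% CIs.

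State the fallback in advance: if the model does not converge, or if the slope variance is estimated at zero, report the random-intercept model, say that this was done, and add a subject-clustered robust CI as a supportive result. The zero-variance case must be covered because it could be common (step 7). The robust CI should stay supportive, since it did not reach nominal coverage.

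The cost is wording in two places, with no new data. When slopes do not differ, the SE is up to about 6% larger. The t quantile adds 1.684/1.645 − 1 = 2% at 40 degrees of freedom, or 1.812/1.645 − 1 = 10% if only 10 are available.

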8.4.3 Holter ECG Monitoring

25-hour Holter monitoring will be conducted on specified days to collect ECG data for QTcF assessment. These data will not immediately be visible to the site investigator and staff. The Holter recordings will be transmitted to the selected ECG core laboratory for analysis. ECG extractions for QTcF analysis will be taken at the same nominal timepoints as the PK draws. All ECGs will be measured after a 10 min rest in the supine position prior to the PK draws.

In Part A, continuous 12 lead ECG Holter monitoring will be performed for 25 hours on Day 1 from 1 hour pre-dose through 24 hours post-dose.

In Part B, continuous 12 lead ECG Holter monitoring will be performed for 24 hours on Days 1 and 5 from 1 hour pre-dose through 24 hours post-dose.

Full details of all procedures relating to the ECG collection are contained in the SOM and/or Holter monitoring manual.

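### The pooled concentration-QTcF model has no Holter-day-within-subject effect for the 18 Part B subjects, so its 90% CI can be too narrow if KAE609 accumulates and QTcF change varies between days

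*SAP*

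**What the plan says.** The Holter ECG paragraphs of SAP 7.2 and Protocol 12.4.2 describe the same model. The outcome is change from baseline in QTcF. On the fixed effects, "KAE609 plasma concentration will be a covariate, and time a categorical variable". On the random effects, "A random intercept for each subject will be specified". Both parts enter one model: "Data from the SAD and MAD parts of the study will be pooled for this assessment". For controls, "Placebo subjects will be included in the analysis with a plasma concentration of 0". The result to be reported is the placebo-corrected effect, and "the two-sided 90% confidence interval will be extracted from the model at the geometric mean maximum plasma concentration for each treatment".

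Protocol 8.4.3 sets the recording days. In Part A, "continuous 12 lead ECG Holter monitoring will be performed for 25 hours on Day 1". For the multiple-dose part: "In Part B, continuous 12 lead ECG Holter monitoring will be performed for 24 hours on Days 1 and 5". Each Holter day yields several readings, since "ECG extractions for QTcF analysis will be taken at the same nominal timepoints as the PK draws".

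Neither document mentions a day-level effect, a residual covariance structure or a robust standard error. Neither defines the baseline for Day 5 or says whether categorical time is crossed with day. Protocol 12.4.4 plans no sensitivity analysis. SAP 7.2 announces a separate cardiac safety report, which is not among the documents.

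**The concern.** In Part B, readings cluster at two levels: within a Holter day, and two days within a subject. The planned model has only the subject level, so it treats readings as independent given the subject. Whatever is particular to one subject on Day 5 is shared by all of that day's readings, but the model handles it as separate errors.

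The choice of baseline matters too. If Day 5 is measured against its own pre-dose value, the error in that value is common to every Day 5 reading and adds to the day component. If the Day 1 baseline serves both days, its error is common to the whole subject and the subject intercept absorbs it.

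The omission affects the slope only when concentration also differs between the two days within a subject. Accumulation under dosing every 24 hours would produce that difference.

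At stake is the only placebo-corrected QTcF estimate with a CI that the visible plan describes. QTcF belongs to the primary safety endpoint, this is the first iv study, and Protocol 4.1 notes a hERG signal (with no QTcF effect seen so far with oral dosing). An interval that is too short could suggest an effect that is absent, or exclude one with too much confidence.

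**Working it through.** **The plan's own figures.** The plan gives no precision or power for this model. Its sample-size figures concern adverse-event detection (for example 1 − 0.8^6 = 0.738, matching the stated 74%) and do not bear on it. The headcount reproduces: 5 × 8 + 2 × 9 = 58.

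**Where the gap lies.** Part A has 40 subjects and 40 subject-days. Part B has 18 subjects and 36 subject-days. By the Part A PK schedule there are 7 post-dose readings per day (10 min to 24 h), plus one at 2 min in the bolus cohorts A1, A2 and B1. The Part B table is not in the supplied text, so the same times are assumed there.

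- Part A: 16 × 8 + 24 × 7 = 296 readings
- Part B: 9 × 2 × 8 + 9 × 2 × 7 = 270 readings

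Part B is 31% of subjects (18/58) but 48% of readings (270/566). SAP 1.4 names both five and four Part A cohorts; four would make N 50 and would not change the conclusion.

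**Model.** For subject i, day j, time k:

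- Planned: Y = time_k + β·C_ijk + u_i + e_ijk
- With the day level: Y = time_k + β·C_ijk + u_i + v_ij + e_ijk

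No treatment term is listed, so the placebo-corrected effect at Cmax is β × Cmax with half-width 1.645 × SE(β) × Cmax. Any understatement of SE(β) carries over in proportion.

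**Mechanism by hand.** Assume day SD 5 ms, residual SD 5 ms and 7 readings per day, and ignore fixed-effect degrees of freedom.

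- True variance of a subject's Day 5 minus Day 1 mean: 2 × (25 + 25/7) = 57.1, SD 7.6 ms.
- Within-subject sum of squares. Part A: 40 × 6 × 25 = 6,000. Part B: 36 × 6 × 25 + 18 × (7/2) × 57.1 = 5,400 + 3,600 = 9,000.
- Residual variance the planned model would estimate: 15,000 / (240 + 234) = 31.6.
- Its variance for the day difference: 2 × 31.6/7 = 9.0, SD 3.0 ms.

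The planned model understates the SD of the between-day contrast by a factor of about 2.5. It overstates the SD of within-day contrasts by √(31.6/25) = 1.12. The net effect depends on how much of the slope's information comes from the between-day contrast.

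**Why half-life decides.** With mono-exponential decline and r = 2^(−24/half-life), the Day 5 concentration relative to Day 1 at the same time after dose is 1 + r + r² + r³ + r⁴. This is 1.07 at 6 h, 1.33 at 12 h, 1.94 at 24 h and 2.43 at 36 h.

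**Simulation 1** (600 runs per case, no drug effect; Monte Carlo SE 1.2 to 1.9 points). Assumed: Part A doses 10 to 210 mg, bi-exponential PK with 25% CV, residual SD 6 ms, subject and day SD 5 ms each (between-day correlation 25/50 = 0.5). Percentage of 90% CIs for the slope that exclude zero:

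| Model | 12 h | 24 h | 36 h |
|---|---|---|---|
| Planned | 9.3 | 15.2 | 29.2 |
| + fixed day | 9.3 | 11.0 | 25.5 |
| + fixed day and random slope | 5.7 | 9.3 | 20.2 |
| Subject and day-within-subject intercepts | 9.8 | 11.0 | 11.0 |

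With subject/day SDs of 6.1/3.5 ms (correlation 0.75) the planned model gives 10%, 13% and 24%. With no day variation it gives 12%. At 36 h and 5/5 ms the true SD of the slope is 1.63 times the reported SE.

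**Simulation 2** (1,000 runs per case). Assumed: 7 readings per day, residual SD 5 ms, PK CV about 30%, time coded as time post-dose or as day-by-time. Coverage of the nominal 90% CI under the planned model (ranges span the two codings):

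| Half-life | Day SD 3 ms | Day SD 5 ms | Day SD 8 ms |
|---|---|---|---|
| 6 h | 0.89 | 0.91–0.92 | 0.94–0.95 |
| 12 h | 0.90–0.91 | 0.90–0.92 | not run |
| 18 h | 0.87–0.89 | 0.82–0.87 | not run |
| 24 h | 0.82–0.85 | 0.73–0.80 | 0.64–0.74 |

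With no day variation, coverage is 0.87 to 0.88. With the day-within-subject intercept it is 0.86 to 0.91 in every scenario. Crossing time with day helps at 24 h but does not close the gap: at day SD 5 ms, coverage is 0.80 under the planned random effect and 0.90 with the day intercept added.

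**The case against.** A reader might infer that the model treats same-day readings as plainly independent. It does not: the subject intercept gives all of a subject's readings a common correlation, and in Part A it is also the day intercept. A model that ignores clustering altogether covered only 0.51 to 0.60 in Simulation 2, far worse than the planned one.

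A reader might also infer that the CI will be too narrow. The documents do not support that. Half-life and day SD are not visible, and PK sampling to 120 h and Day 8 does not establish a long half-life. At 12 h or less the interval is about right or slightly wide. The no-day-variation floor in Simulation 1 is already 12%, so 13 to 15% at 24 h is a small excess there. At a day SD of 2.5 ms, a smaller simulation (150 runs per case) found 10%, 14% and 11% at 12, 24 and 36 h, against 11%, 14% and 7% with the day intercept.

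In milliseconds the shortfall may be modest. In that smaller simulation's extreme case (36 h, 5/5 ms, 23% false positives), the reported half-width at the 120 mg Day 5 Cmax was 3.3 ms against about 4.4 ms needed, a gap of about 1.1 ms. In Simulation 1 a fixed day term does as well as the day intercept at 24 h.

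Finally, both documents call this modelling exploratory, with no hypothesis or margin. The stopping rules in Protocol 9.1.4 use individual QTcF values, and outlier tables are planned as well.

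All of this stands and limits the size and importance of the point. It does not remove the gap: nothing visible in the plan protects the interval if the drug does accumulate.

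**Conclusion.** The point holds in a conditional form. For the 18 Part B subjects the model omits the extra same-day correlation; the 40 Part A subjects are unaffected. The 90% CI is too narrow only if concentrations rise from Day 1 to Day 5 and subjects' QTcF change varies between days.

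Under assumed inputs, the false-positive rate against a nominal 10% is about 10% at a 12 h half-life. At 24 h it is about 15% in Simulation 1, and 15 to 27% in Simulation 2 for day SDs of 3 to 5 ms. At 36 h it is 25 to 29% with a day SD of 3.5 to 5 ms. At 36 h a fixed day term does not repair it (26% remains).

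A reader might go further and infer that the primary safety conclusion or dose escalation rests on a faulty interval. The documents do not support that: no decision rule uses this CI. Importance is moderate, and the change is worth making because it is cheap and almost harmless when not needed.

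**What to change.** In SAP 7.2 and Protocol 12.4.2, replace the random-effects sentence with: *Random intercepts for subject and for Holter day within subject (Part B Days 1 and 5) will be specified; if the day component is estimated at zero, the model reduces to the subject intercept.*

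In the same edit, state which baseline applies to Day 5 and whether categorical time is crossed with day, since both change how much day-level correlation there is to model.

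The cost is a sentence or two in each document and one extra random term in the program, with no new data or subjects. Under Protocol 14.1 the protocol wording needs a written amendment. The statistical price is a somewhat wider CI when day variation is present, and a day variance estimated from only 18 subjects.
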